In the space below, provide a written summary of both unanticipated problems* and available information regarding adverse events since the last review (e.g., initial review or annual/continuing review). The amount of detail provided in such a summary will vary depending on the type of research being conducted; in many cases, such a summary could be a brief statement that there have been no unanticipated problems and that adverse events have occurred at the expected frequency and level of severity as documented in the research protocol, the informed consent document, and investigator's brochure (if applicable). **The summary must include the PI's assessment whether the problems/adverse events warrant changes to the protocol, consent process, or risk/benefit ratio.**

Note: It is the IRB's expectation that all unanticipated problems involving risk to subjects or others or related deaths requiring prompt reporting are submitted in the appropriate time frame (See Policy [\[PDF\]](#)). Your response to this Annual/Continuing Review is considered assurance that all prompt reportable problems/adverse events have been submitted for IRB review.

*For multisite studies, the written summary should describe external events determined to be unanticipated problems involving risk to subjects or others.

5. Subject Info To-Date

Our records for the previously approved IRB application indicate the **IRB approved estimate** of subjects to be enrolled (or records/specimens reviewed) is:

60

Enter the number of enrolled subjects (or records/specimens reviewed) that **have not been previously reported** to the IRB

0

Our records for the previously approved IRB application indicate the previous total # of subjects enrolled (or records/specimens reviewed) since activation of the study is:

9

The new total number of subjects enrolled (or records/specimens reviewed) since activation of the study: **10**

Please review the Project Info section for the IRB approved estimate of subjects to be enrolled (or records/specimens reviewed). If this new total exceeds your approved estimate of subjects to be enrolled (or records/specimens reviewed), please update the number in the field for Number of Human Subjects in the Project Info section.

6. Data and Safety Monitoring Board (DSMB)/Plan (DSMP)

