Study Proper. This will be a double blind randomized controlled trial. All subjects will receive both TBS and sham TMS in a randomized manner with counter balancing. The TBS session and sham TMS will be done on separate days. Subjects will be randomized to receive either TBS first and sham TMS second, or sham TMS first and TBS second. The PI ([name]) will be blind to the randomization status and will supervise the TMS session. Subjects will also remain blind to the randomization status. This will be facilitated by the Magventure Active/sham TMS coil which has been shown to maintain integrity of blinding in subjects regarding group assignment. We will recruit 30 patients from one of these clinics - the Bluegrass Clinic, SMART clinic in psychiatry and Beyond Birth Clinic in Psychiatry. All of them would receive TBS and sham TMS on separate days. The Bluegrass HIV clinic has a closely monitored population of PLWHA patients. The PI ([name]) and a research assistant would interface with [name] at the Bluegrass HIV Clinic on a weekly basis and with [name] on a daily basis to recruit patients for this study. The PI ([name]) and the research assistant will also interface with [name] (who heads the SMART clinic and Beyond Birth Clinic) on a weekly basis. If interested in participating, we will provide subjects with information and seek informed consent before proceeding with the study.

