Pertaining to the modification of study design - For subjects who have already participated in our trial and received one TMS session, we will inform them about this modification and ask them if they would be interested in coming back to receive another session of TMS (which may be active or sham, they will receive the opposite of what they got initially). The randomization procedure will be supervised by [name] this will be factored into the randomization counterbalancing procedure. We will educate participants who have completed the study previously on the modification of study design and offer them the modified consent form to read and sign if they are interested in participating in the third day of the study.

No flyers will be created for the pilot study. For the main study, we will create study flyers for providers at three clinics. These will list inclusion and exclusion criteria for the study as well as contact numbers for the PI ([name]) and research assistant involved in the study.

Attachments

Attach Type	File Name
Advertising	64473_business_card PR edit STAMPED.pdf
Advertising	Bell_email.docx
Advertising	Rakesh_Flyer PR STAMPED.pdf

Research Procedures

Describe how the research will be conducted.

- What experience will study participants have?
- What will study participants be expected to do?
- How long will the study last?
- Outline the schedule and timing of study procedures.
- Provide visit-by-visit listing of all procedures that will take place.
- Identify all procedures that will be carried out with each group of participants.
- Describe deception and debrief procedures if deception is involved.

Differentiate between procedures that involve standard/routine clinical care and those that will be performed specifically for this research project. List medications that are explicitly forbidden or permitted during study participation.

Before the study proper, we will run a pilot to validate the attentional bias task. In this pilot, 20 subjects with current or previous history of smoking as well as 20 subjects with no history of current or previous smoking will perform a computerized behavioral task that examines attentional bias to smoking cues versus neutral cues. Subjects will perform the attentional bias task following informed consent. Following informed consent, they will undergo breathalyzer and CO estimation prior to the study session.

Study Proper

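### Voluntary returners from the one-session design enter the counterbalancing, and with no period or cohort term in the models, treatment order can become partly confounded with cohort

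*Combined protocol and SAP*

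**What the plan says.** The Study Design section sets out a two-period crossover: "Subjects will be randomized to receive either TBS first and sham TMS second, or sham TMS first and TBS second". It plans 30 patients, with counterbalanced orders, and says of the interval only that "The TBS session and sham TMS will be done on separate days". No washout, minimum or maximum gap is given, and neither is a block size or stratum.

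The paragraph on the design modification, under Subject Recruitment Methods & Advertising, deals with people already treated once. The team will "ask them if they would be interested in coming back to receive another session of TMS", and "they will receive the opposite of what they got initially". It adds that "this will be factored into the randomization counterbalancing procedure" without describing how. These subjects sign a modified consent form and attend only the third study day.

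The Subject Info To-Date part of the continuation review reports a previous total of 9. For "The new total number of subjects enrolled (or records/specimens reviewed) since activation of the study" it gives 10. It does not separate pilot subjects, one-session subjects and crossover subjects.

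The Attentional Bias and Cigarette craving analyses use fixed effects linear regressions. They name outcomes but no period, sequence, cohort or gap term, and no separate handling of returners. The connectivity analysis compares baseline, post-TBS and post-sham scans within subject. Table 1 has one pre-TBS scan, on Day 1, and has attentional bias and craving measured before and after stimulation on both Days 2 and 3.

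**The concern.** A crossover removes a general change between first and second session by having equal numbers in each order. That works if the change is the same, on average, in both orders. Here two kinds of subject are combined. Returners had their first session before the design changed, chose whether to come back after experiencing it, and have their order fixed by the earlier allocation. New subjects are randomised to an order and are scheduled for both sessions from the start.

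If the combined total is balanced by giving new subjects the order that is short among returners, each order holds a different mix of the two cohorts. Any difference between cohorts in how outcomes move from first to second session then enters the TBS-sham estimate. Such differences could come from smoking level, task familiarity or time since the first visit. The totals would look perfectly balanced, so nothing in the data summary would reveal it.

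**Working it through.** The plan gives no power, alpha or effect size behind the 30, so there is no stated figure to reproduce.

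**Inputs**
- N = 30 (Study Design). Overall order balance of 15:15 is assumed as the outcome of counterbalancing.
- m returners, of whom a had TBS first. Neither is stated. The reported enrolment of 9 to 10 caps m. I use m = 8 as an assumption.
- Period effects (second session minus first, same condition): P_R in returners and P_N in new subjects. A difference of 0.5 SD is an assumption, on the scale of the SD of the within-subject TBS-sham difference.

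**Bias formula**

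The TBS-sham difference is T - P in a TBS-first subject and T + P in a sham-first subject. Sham-first minus TBS-first is m - 2a among returners. Forcing 15:15 makes it -(m - 2a) among new subjects. Averaging over 30:

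bias = (m - 2a) x (P_R - P_N) / 30

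| Returners | New subjects | Imbalance / 30 | Bias at 0.5 SD |
|---|---|---|---|
| 4:4 | 11:11 | 0 | 0 |
| 5:3 | 10:12 | 2/30 = 0.067 | 0.033 SD |
| 6:2 | 9:13 | 4/30 = 0.133 | 0.067 SD |

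The sign depends on which order is in excess. On the same scale the standard error of the mean difference is 1/sqrt(30) = 0.183, so 0.067 is a little over a third of a standard error.

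**How easily imbalance arises**

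If each of 8 returners is equally likely to have had either order, an even split has probability 70/256 = 27%, 5:3 either way 112/256 = 44%, and 6:2 or worse 74/256 = 29%. With 9 returners, an imbalance of 3 or more has probability 0.51, and the average absolute bias is 8% of (P_R - P_N). Differential return adds to this. With 5 subjects per first condition, and return rates of 40% after TBS and 80% after sham (assumptions), the expected split is 2:4 and the bias is 2/30 = 6.7% of the difference.

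**Which model term removes it**

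Simulation: 20,000 runs, 9 returners, SD of difference 1, P_R = 0.5, P_N = 0.

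| Returner split | No term: bias (SE) | Common period term | Cohort-by-period term |
|---|---|---|---|
| 2:7 | 0.082 (0.184) | 0.082 (0.184) | about 0 (0.197) |
| 3:6 | 0.051 (0.181) | 0.051 (0.181) | about 0 (0.185) |

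The formula gives 5/30 x 0.5 = 0.083 and 3/30 x 0.5 = 0.050, which agrees. A common period term does nothing, because the overall order is already 15:15.

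**Separate allocation alone is not enough**

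With new subjects at 11:11, returners at 6:2 and no period terms, the bias is 4/30 x P_R. The returners' own imbalance stays in the estimate until period terms are added.

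**The case against.** The strongest reply is that the problem is conditional. A reader might infer that the plan ties treatment order to the gap. It does not. The recruitment text still describes randomisation to one arm or the other, so returners' first condition appears to have been randomised and both orders can occur among them. An even split gives no bias. Subjects are also blind, which limits return that depends on condition, and self-selection unrelated to condition does not by itself bias a within-subject contrast. All of this stands.

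A reader might also infer that the gap is known to be much longer, or that new subjects are certainly steered to the opposite order. A longer gap is a fair inference from the design change, but no interval is stated for either group. Offsetting allocation is the natural reading of the sentence on counterbalancing, but the mechanism is not described.

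Same-day pre-stimulation measures would absorb level drift in attentional bias and craving if change were modelled, leaving only a gap effect on the within-session change. The analysis text does not say that change is modelled. For connectivity, the Day 1 scan cancels in a direct post-TBS versus post-sham comparison, though not in a comparison of either condition with baseline.

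It is tempting to say that non-returners' data are lost. No complete-pair rule is stated for the behavioural outcomes, so that depends on the model chosen. It is equally tempting to express 0.067 SD as a share of the cited craving effect of 0.471. That is a literature meta-analytic value whose SD may be on another scale, so the ratio is not reliable.

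**Conclusion.** The concern holds as a conditional risk. The plan mixes voluntary returners into one counterbalancing scheme by an undescribed mechanism, and names no model term that would separate cohort from order. Bias requires three things together: unequal orders among returners, offsetting allocation of new subjects, and a period effect that differs between the cohorts. The documents establish none of the three, and they exclude none.

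Under the assumptions of 8 returners and a 0.5 SD difference, the size is 0 to about 0.07 SD for splits from 4:4 to 6:2. That is modest beside the standard error. It would matter more if fewer than 30 were analysed, because the divisor is the number analysed. The remedy is cheap enough that the change should be made.

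**What to change.** 1. State the number of returners, their orders, the interval between their two sessions, and exactly how they enter the counterbalancing.
2. Randomise new subjects 1:1 in their own blocks, with returners as a separate stratum that is not used to balance them.
3. Add period and cohort-by-period terms to the attentional bias and craving models. This must accompany step 2, since separate allocation leaves the returners' own imbalance in place.
4. Adjust for each session's pre-stimulation score.
5. Keep first-session data from subjects who do not return. With one score per session this needs a random subject effect, because a fixed subject effect would take no treatment information from a single session.
6. For connectivity, rely on the post-TBS versus post-sham contrast, since a returner's Day 1 scan predates the gap. Drift between the two post-session scans does not cancel, so step 7 applies here too.
7. Report the TBS-sham estimate with and without returners.

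The cost is a revised randomisation list for new subjects, a few model terms, a slightly larger standard error (0.184 to 0.197 in the 2:7 case above) and possibly a small overall order imbalance. If enrolment is over, steps 1 and 3 to 7 can still be done.

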Theta burst stimulation (TBS). A new TMS paradigm, theta burst stimulation (TBS), uses theta frequency stimulation at gamma frequency. TBS is different from other TMS frequencies in that it delivers significantly more dosing pulses over the same time period. TBS is safe and was approved for MDD by the FDA in 2019. To the best of our knowledge, there has been only a single clinical study that utilized theta burst stimulation for smoking cessation. Four sessions of intermittent TBS (iTBS) added to Cognitive Behavioral Therapy (CBT, twice weekly sessions for three weeks) (56) were delivered. Participants (N=74) received either iTBS (600 pulses) or sham TMS. The groups did not differ in number of cigarettes smoked or scores on Fagerstrom Test for Nicotine Dependence (FTND). At three months of follow-up, the iTBS group had 19 subjects reporting abstinence while 19 had relapsed. The sham TMS group had 10 subjects abstinent and 26 subjects who had relapsed. To the best of our knowledge, no studies used TBS or other rTMS for smoking cessation in PLWHA.

TMS for modulation of cognitive performance including attentional bias. TMS has also been used to modulate cognitive performance, to accelerate mechanisms of smoking cessation across various studies (57, 58). Previous TMS treatment studies for smoking cessation have included cognitive outcome measures including delayed discounting (59, 60) and cigarette cue induced craving assessed using an analogue scale (61). It is plausible modulation of these cognitive paradigms by TMS could contribute to craving reduction and behavioral changes in cigarette use. Multiple previous studies support the existence of an attentional bias towards smoking related cues compared to neutral cues in tobacco use disorder(62). Modulation of attentional bias has been attempted in MDD. To the best of our knowledge, no study has used TMS to modulate attentional bias in subjects with smoking behavior.

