A sequential timeline of assessments and interventions are shown in table one. After informed consent, subjects will get an MRI brain scan at the Magnetic Resonance Imaging and Spectroscopy Center (MRISC) affiliated with University of Kentucky. Subjects will also be escorted to the MRISC at the UK Medical Center by the PI ([name]) and a research assistant. Subsequently, neuroimaging data (MRI brain) will be acquired using a Siemens 3-Tesla (3T) PRISMA MRI scanner as described under Data Collection below. This will happen on day 1. Then, on days 2 and 3, subjects will be scheduled for three hour experimental sessions at the TMS Suite at [name]. During these three hour sessions, subjects will perform the tobacco craving questionnaire (TCQ) while performing stress induced craving paradigm, attentional bias task and delayed discounting task. These activities will last an hour. Then we will obtain active motor threshold (AMT) from the first dorsal interosseous (FDI) muscle and left motor cortex, following which we will administer either a session of theta burst stimulation (TBS) for 9 minutes at 80% active motor threshold (AMT) or sham TMS to the left dorsolateral prefrontal cortex using a figure 8 coil and MagVenture MagPro x100 device (MagVenture A/S, Denmark), with TMS coil position stabilized using BrainSight (Rogue Solutions, Montreal, Canada). We will record motor evoked potential before and after the TBS session to assess response (10% increase in MEP to be a cutoff parameter). These activities will last another hour. After the TBS/sham TMS session, subjects will perform TCQ concomitant with the stress induced craving paradigm, attentional bias and delayed discounting tasks. These will last an hour. Then subjects will be transported to MRISC for their post TBS session MRI brain scan in the 3-Tesla (3T) PRISMA scanner.

Table 1

Study Task Study Day Pre- TBS Post-TBS

Urine Pregnancy Test 1

MRI brain at MRISC (Pre-TBS) 1

Exhaled CO 2 and 3 X

Motor Threshold 2 and 3 X

Eye tracking to measure AB 2 and 3 X X

Delayed Discounting Task 2 and 3 X X

Tobacco Craving Questionnaire 2 and 3 X X

TMS Side Effects Questionnaire 2 and 3 X

Treatment Acceptability Questionnaire 2 and 3 X

MRI brain at MRISC (Post-TBS) 2 and 3 X

Attachments

Subject Recruitment Methods & Advertising

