Following informed consent, the subject will be asked to come to MRISC for a MRI brain scan contingent on the investigative team obtaining a slot for this. The PI will coordinate with staff at MRISC to obtain a MRI slot. Subjects will also be escorted to the MRISC at the UK Medical Center by the PI ([name]) and a research assistant. Neuroimaging data (MRI brain) will be acquired using a Siemens 3-Tesla (3T) PRISMA scanner as described under Data Collection below. This will happen on day 1 and will last an hour. Then, on days 2 and 3, subjects will be scheduled for three hour experimental sessions at the TMS Suite at [name]. During these three hour sessions, subjects will perform the tobacco craving questionnaire (TCQ) while performing stress induced craving paradigm, attentional bias task and delayed discounting task. These activities will last an hour. Then we will obtain active motor threshold (AMT) from the first dorsal interosseous (FDI) muscle and left motor cortex, following which we will administer either a session of theta burst stimulation (TBS) for 9 minutes at 80% active motor threshold (AMT) or sham TMS to the left dorsolateral prefrontal cortex using a figure 8 coil and MagVenture MagPro x100 device (MagVenture A/S, Denmark), with TMS coil position stabilized using BrainSight (Rogue Solutions, Montreal, Canada). We will record motor evoked potential before and after the TBS session to assess response (10% increase in MEP to be a cutoff parameter). These activities will last another hour. After the TBS/sham TMS session, subjects will perform TCQ concomitant with the stress induced craving paradigm, attentional bias and delayed discounting tasks. These will last an hour. Then subjects will be transported to MRISC for their post TBS session MRI brain scan in the 3-Tesla (3T) PRISMA scanner.

Motor Threshold

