Motor threshold (MT) is defined as the TMS pulse amplitude needed to elicit an EMG response of 50 μ V peak-to-peak average amplitude in a target muscle. MT is the standard in the field for determining the intensity of TMS for everyone to reduce seizure risk. The MEP for the right first dorsal interosseous (FDI) will be measured with EMG. The scalp region producing the largest amplitude MEP will be identified. At that scalp location, we will determine the TMS intensity eliciting average MEP amplitude of 50 μ V peak-to- peak in the first DI muscle using an amplitude titration procedure (at least 5/10 trials). Individual MT will be used to determine the intensity of theta burst stimulation for everyone, as recommended by safety guidelines.

TBS application

A magnetic coil will be placed on the scalp and held in place with frameless stereotaxic equipment, using a sophisticated method of coil placement that will coregister scalp positions directly onto an average brain template. This Frameless Stereotaxic System Brainsight offers real-time three-dimensional display of cortical localization as the TMS coil is moved across the scalp. This will be used for coil positioning. This system uses a programmed robot arm to precisely position the TMS coil, and maintain its position, within 1 mm of the brain target chosen. Earplugs will be worn to protect hearing and low-volume white noise will be played through TMS-compatible headphones to mask the sound of the coil clicks. The intensity of the stimulation will be 120% of resting motor threshold as reported in a previous studies. The participant will be seated comfortably with headphones and earplugs to protect the subject's hearing. Before applying TBS or sham TMS, we provide subjects without scalp hair the option to apply 5% lidocaine spray (aspercreme) that is available over the counter to the left frontal quadrant of their scalp. This would minimize discomfort if any they feel during the stimulation. They would have the option to refuse as well.

Stress induced craving paradigm

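### The plan gives two incompatible theta burst intensities, 80% of active motor threshold and 120% of resting motor threshold, and does not say which governs

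*Combined protocol and SAP*

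**What the plan says.** Three places in the combined protocol and SAP bear directly on intensity.

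- **Study Design (Study Proper) and Research Procedures (Study Proper).** Near-identical text in both says "Then we will obtain active motor threshold (AMT) from the first dorsal interosseous (FDI) muscle and left motor cortex", and then that the subject receives either sham or "theta burst stimulation (TBS) for 9 minutes at 80% active motor threshold (AMT").
- **Research Procedures, TBS application.** "The intensity of the stimulation will be 120% of resting motor threshold as reported in a previous studies".
- **Research Procedures, Motor Threshold.** This defines a motor threshold by a 50 microvolt response, found "using an amplitude titration procedure (at least 5/10 trials"). It does not say whether the muscle is at rest or contracted. It also gives the reason for using a threshold: "MT is the standard in the field for determining the intensity of TMS for everyone to reduce seizure risk".

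Table 1 of Study Design has a single row, "Motor Threshold 2 and 3 X", which names neither threshold type. No supplied text says that a resting threshold is obtained.

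**The concern.** A trial of one active intervention needs one rule for its intensity. Here the operator could follow either of two rules, and a reader cannot tell which was planned. A positive or a null result could not be tied to a known stimulation intensity, and the session could not be reproduced. This matters more because the Background presents the study as testing an adequately dosed session and as supplying data for a grant resubmission.

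The plan also treats intensity as a safety parameter. The Motor Threshold text links it to seizure risk, and Potential Risks & Benefits commits the study to guidelines that cover intensity. A plan that relies on an intensity rule should contain only one.

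**Working it through.** **1. Do the statements describe the same thing?** Yes. The objectives and Study Design describe one active condition, a TBS session to the left dorsolateral prefrontal cortex, compared with sham. No text limits either intensity to a subset of subjects or sessions, and neither is marked as superseded.

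**2. Does anything else in the supplied text settle it?**

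| Place | What it offers |
|---|---|
| TBS application | Cites earlier studies for 120%, without naming them or giving their intensities |
| Background, Theta burst stimulation | Describes the one earlier TBS smoking study: "Participants (N=74) received either iTBS (600 pulses) or sham TMS". Pulses are given, intensity is not |
| Objectives | 1800 pulses, no intensity |
| Subject Recruitment, modification of study design | "For subjects who have already participated in our trial and received one TMS session", a second and opposite session is offered. No change of intensity is mentioned |
| Attentional bias, craving and connectivity analyses | Intensity is not used |

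None of these gives precedence to either rule.

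**3. Does the measurement text settle it?** The only threshold named as obtained is the active one, which fits the 80% wording. The titration procedure and the Table 1 row leave the muscle state open, so the procedure cannot be assigned to one rule. If it is meant for one state only, the other rule has no described measurement. If it is a generic titration for either state, what is missing is the muscle state.

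**4. Could the two be one intensity in different words?** Write RMT for resting and AMT for active motor threshold.

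Ratio of outputs = (1.20 × RMT)/(0.80 × AMT) = 1.5 × RMT/AMT

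The rules agree only when RMT/AMT = 0.80/1.20 = 0.667, that is, when the active threshold is 1.5 times the resting one.

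The documents give no RMT/AMT. The values below are assumptions, used only to show scale.

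| Assumed RMT/AMT | 120% RMT divided by 80% AMT |
|---|---|
| 0.667 | 1.00 |
| 1.0 | 1.50 |
| 1.1 | 1.65 |
| 1.2 | 1.80 |
| 1.667 (AMT/RMT = 0.6) | 2.50 |

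Whenever RMT is at least AMT, the gap is 1.5-fold or more, which is too large to be rounding.

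**5. How many sessions are affected?** The continuation review form gives 9 previously reported subjects and 0 new, but a new total of 10, and it does not separate the pilot from the study proper. With two stimulation sessions per subject (days 2 and 3), there are at most 2 × 9 = 18 to 2 × 10 = 20 session records. At most 9 to 10 of these are active.

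**The case against.** The contradiction itself is hard to dispute. The best case on the other side is about how much it matters.

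- **The harm is limited.** The documents show neither value to be unsafe and give no limit to test them against. They do not show that delivery was mixed. The planned models do not use intensity, so one rule applied throughout would not bias the active-versus-sham comparison within subjects. The file is marked closed, so no future session is protected. All of this stands, and it confines the point to interpretation, reproducibility and the clarity of the safety rule.
- **The within-subject reassurance has its own limit.** Subjects treated before the design modification were only invited back, so some may have had a single session. This also stands.
- **The procedure may be generic.** One titration method could serve for either threshold. That is a fair reading, and it reduces the measurement gap to an unstated muscle state. The two percentages still conflict.
- **The size rests on an assumed ratio.** Correct. Only the formula and the equality point follow from the documents.
- **Other material may settle it.** Consent forms, device forms and files attached as protocol were not available, and some pages were removed before review. They may state an intensity, but the text reviewed here would still contradict itself.

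**Conclusion.** The concern holds. The current text gives two incompatible rules for the intensity of the only active intervention, and nothing supplied ranks them, so the plan cannot be followed as written. The rules coincide only at RMT/AMT = 0.667. They differ by at least 1.5-fold on the assumption that resting threshold is no lower than active threshold. The finding rests on the wording and would stand without that assumption.

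It must be fixed because it concerns what the active condition was. It is not a finding that either intensity is wrong or unsafe, that subjects received different intensities, or that the primary contrast is biased.

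**What to change.** The investigator should reconcile Study Design, Research Procedures (Study Proper) and TBS application so that they state one intensity and one threshold type. The Motor Threshold subsection and the Table 1 row should then name that threshold and state the muscle state during titration. Which value is right is for the investigator to establish.

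For subjects already treated, the session records should be checked for the threshold type and percentage actually used, and these should be reported. If a mixture is found, disclose it; otherwise state that one rule was applied throughout. Because the file is closed, the clarification belongs in the final report and in any publication.

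The cost is a wording change and a check of at most 18 to 20 session records, with no extra visits.
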